## Biobank

**Study Biobank:** Frozen plasma samples for FGF19 and C4 are stored in a biobank for analysis once the last participant has finished the study. After analysis, surplus plasma is re-frozen and stored for a period of maximum 15 years, but only if the subject has given consent to the biobank for future scientific work described below. Analysis of bile acid species including C4 is done in Paris (see cooperating departments, page 3). **Biobank for future scientific work:** This is created for future, yet unspecified scientific work. 22mL blood is required to be stored as 4mL plasma and 10mL EDTA-blood. Furthermore, a stool sample is collected for this biobank. Separate informed consent is obtained for the biobank. Consent may be withdrawn and the samples are then destroyed. This biobank is stored for a period of 15 years and then destroyed. The biobank will not be given to the third party. Data security is monitored by the Danish Data Security Agency.

## Study medication

### Colesevelam

Colesevelam is registered for treating hypercholesterolemia; however, it is extensively used off-label as a sequestrant treating bile acid diarrhoea (13, 14, 37, 38). The treatment effect is comparable to that of colestyramine and it is considerably better tolerated (13, 38). Colesevelam tablets are bought from Sanofi-Aventis by the Hospital Pharmacy of the Capital Region of Denmark. The Pharmacy encapsulates colesevelam and placebo tablets (Capsugel® DBcaps®, size AAA) in accordance with Good Distribution Practise and Good Manufacturing Practise and documents this.

**Purpose:** the active arm of the double-blinded randomised intervention.

**Dose:** We strive for a standard dose of three capsules each of 625mg twice daily taken before breakfast, lunch, or dinner. To avoid drop-out due to dose-related adverse reactions such as nausea, constipation, and vomiting we use dose escalation and titration.

Start dosage: 2 tablets twice daily for two days. If the subject has no or limited side effects, the dose is increased to 3 tablets twice daily. In case of severe constipation, nausea, or vomiting the dose may be decreased (to one capsule twice daily). Minimum dose is one capsule twice daily. Dosing once daily is not allowed. All subjects are contacted by telephone on day 2–3 to ensure dose escalation if possible. If the dose is changed the subjects is contacted again 2–3 days afterwards to follow up.

Communication regarding dose and registration of AEs is kept between the subject and a study nurse does not partake in endpoint registration nor in reporting of the study. If the nurse needs advice from a doctor, this is first sought from a doctor who is not affiliated with the study; ie. not from an investigator. In matters regarding possible serious adverse events, the decision of emergency unblinding, study participation etc. the investigator must be involved.

**Side effects to colesevelam:** See the exert below from Summary of Product Characteristics (updated 28.11.2018).

#### 4.8 Undesirable effects

##### Summary of the safety profile

The most frequently occurring adverse reactions are flatulence and constipation, found within the gastrointestinal disorders system organ class.

##### Tabulated list of adverse reactions

In controlled clinical studies involving approximately 1400 patients and during post-approval use, the following adverse reactions were reported in patients given Cholestagel.

The reporting rate is classified as very common ( $\geq 1/10$ ), common ( $\geq 1/100$  to  $< 1/10$ ), uncommon ( $\geq 1/1,000$  to  $< 1/100$ ), rare ( $\geq 1/10,000$  to  $< 1/1,000$ ), very rare ( $< 1/10,000$ ) and not known (cannot be estimated from the available data).

Nervous system disorders
Common: Headache
Gastrointestinal disorders
Very common: Flatulence*, constipation*
Common: Vomiting, diarrhoea*, dyspepsia*, abdominal pain, abnormal stools, nausea, abdominal distension
Uncommon: Dysphagia
Very rare: Pancreatitis
Not known: Intestinal obstruction*,**
Musculoskeletal and connective tissue disorders
Uncommon: Myalgia
Investigations
Common: Serum triglycerides increased
Uncommon: Serum transaminases increased

\* see section below for further information

\*\* adverse reactions from post-marketing experience

##### \*Description of selected adverse events (continued from exert)

The background incidence of flatulence and diarrhoea were higher in patients receiving placebo in the same controlled clinical studies. Only constipation and dyspepsia were reported by a higher percentage among those receiving Cholestagel (colesevelam), compared with placebo.

The incidence of intestinal obstruction is likely to be increased among patients with a history of bowel obstruction or removal.

Cholestagel in combination with statins and in combination with ezetimibe was well tolerated and the adverse reactions observed were consistent with the known safety profile of statins or ezetimibe alone.

## Placebo

Matrix placebo tablets (17mm size) with same capsule (Capsugel® DBcaps®, size AAA) making these identical to the colesevelam capsules.

The tablet matrix does not affect bowel function. Constituents are as follows per tablet:

- Lactose monohydrate 330mg
- Potato starch 335mg
- Gelatine 12mg

- Magnesium stearate 3.5mg
- Talc 31.5 mg

The placebo capsules (Capsugel® DBcaps®, size AAA) dissolve in the stomach giving a negligible delay in availability of colestevlam of 2–3 minutes.

No side effects are expected from the placebo tablets.

## Study plan

### Pre-screening – Written invitation

This has two steps:

1. Eligible participants as deemed by inclusion and exclusion criteria are either given or send the written invitation by the Gastroenterological department when referred for SeHCAT or send from the Clinical Physiological Nuclear Medicine department to referred patients. All pre-screened participants are anonymously registered on a pre-screening list.
2. At the first SeHCAT visit a sub-investigator asks the potential subject, if the written invitation is received, read, and understood. **Further**, we ask if they consider participation and/or would like further information from the investigator (doctor).

The investigator assess eligibility, informs and may include the patient as specified under “Ethics”. If an eligible subject opts to participate, this visit (first SeHCAT visit) is called **Study visit 1**.

### Study visit 1 – Inclusion and start of baseline registration

#### Study Day 1.

After inclusion, a blood sample for the study biobank is drawn. This sample is used to assess the concordance between repeated tests, and we register the given conditions for this sample to explore how sampling time, fasting, medication etc. affect the C4 sample.

#### Case Record Form

At inclusion the (sub)investigator creates an electronic Case Record Form for the study subject to document:

- Medical history
  - Physical status
  - Medication of interest: antidiabetic, analgetic, anti-hypercholesteremia, anti-diarrhoea, laxatives, systemic glucocorticoids, recent (3 mo.) systemic antibiotics.
  - Prior medical and surgical history

- Results within 12 months of any diagnostic workup regarding diarrhoea
  - Microbiological stool samples
  - Fecal-calprotectin
  - Fecal-elastase
  - Biochemical analyses for lactose intolerance, coeliac disease, thyrotoxicosis
  - Endoscopies, regarding coeliac disease and inflammatory bowel disease including histology
  - Breath tests for malabsorption or bacterial overgrowth
- Use of tobacco and alcohol
  - Baseline blood analyses (ALT, ALP, bilirubin, amylase)
  - Weight (measured) and height

The (sub)investigator needs access to the subject's medical file and chart. This is specified in participant information and is given in the written informed consent.

All subjects complete the baseline questionnaires (Q-base) consisting of

- 1) Short Form 36 version 2 (SF36v2 two week recall) on HRQoL
- 2) Gastrointestinal Symptom Rating Scale (GSRS)
- 3) Short Health Scale focused on the gastrointestinal effect on HRQoL.

We ask all subjects if they as a voluntary supplement would opt to answer the questionnaires addressing sexual dysfunction due to chronic diarrhoea. If yes; we send the questionnaire to the subject to answer at home before Visit 2 and again at the six-month follow-up.

All subjects are given:

1. the baseline diary
2. a kit for stool sampling at home

### ***Optional stool sample for biobank for future scientific work***

The subject may opt to take a collection kit for stool sample at home on study day 6 or 7 to make 75-Se radiation negligible. The sample is immediately placed in the subjects' -18 – -23°C freezer. The subject brings the sample on study visit 2 for placement in a - 80°C freezer. If the subject continues to treatment, he/she may opt for a second sample taken on treatment day 18–20 and deliver it on Visit 3.

Stool sampling is not mandatory for study participation and is only planned if it is feasible according to the individual circumstances.

**Notification to the institution that referred for SeHCAT**

The (sub)investigator e-mails the institution that referred for SeHCAT with instructions to contact the investigator if they find participation inappropriate. This notification is only optional on the condition that the subject consents to the notification.

**Study visit 2 – Assessment of eligibility by stool diary results**

**Study Day 8.** Concurrent with the second SeHCAT visit, all subjects meet in the fasting state, the only exception is drinking still water. Subjects must not ingest alcohol on the day before visit 2.

Fasting blood samples are drawn from all subjects, no later than 10:00 AM.

The blood samples include: 4mL plasma for C4 and for FGF19 analysis (total 8mL). Routine samples for: p-triglycerides, p-cholesterols (total, High and Low-Density Lipoproteins), fasting p-glucose.

Any violation of alcohol abstinence the day before study visit 2 and of pausing statin/fibrate use leads to exclusion as a protocol violation. Minor violations of fasting (drinking thin fluids like coffee or tea, also with milk added) are noted in the CRF and the patient can participate in the study. All other violations lead to exclusion or rescheduling for fasting blood sampling another day.

The (sub)investigator collects the baseline study diary and tallies this.

**Study Diary 1 – baseline**

Subjects are screened for baseline diarrhoea as defined by Hjortswang's criteria:

- $\geq 3$  stools per day or  $\geq 1$  watery stool per day (Bristol Stool form 6 or 7) as a mean of seven days (minimum six days).

The baseline week is the week between the first and second SeHCAT retention test.

The result of the baseline stool diary determines whether the subject objectively has diarrhoea as specified above.

**Subjects without diarrhoea:**

These subjects do not proceed to the intervention, thus, we do not register adverse events for these subjects.

SeHCAT results are registered once available and the subjects are reminded of the six-month follow-up on the subject's medical chart and the aetiology of the subject's health complaints. The follow-up is done by telephone and the questionnaires are distributed electronically, or in special circumstances by mail.

After the six-month follow-up, study participation ends for the subjects without diarrhoea.

**Subjects with diarrhoea:**

This is the ITT population.

Adverse Event registration starts now (study day 8) and includes all subjects with diarrhoea.

The (sub)investigator dispatches the relevant double blinded treatment packet according to the randomisation sequence.

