### **Exclusion criteria**

- Inflammatory bowel disease, including microscopic colitis
- Acute suspected or proven viral gastroenteritis within the recent 4 weeks
- Acute non-viral gastroenteritis within the recent 8 weeks
- Investigator-assessed debilitating chronic disease e.g. WHO performance score 3–5

- Prior treatment with colesevelam
- Treatment with laxatives or anti-diarrhoeal drugs during the study
  - Except for stable dose the last four weeks of psyllium husk and opioids for pain
- Pregnancy
- Breastfeeding women
- Crucial medication that cannot be separated appropriately from colesevelam
  - i.e. taken one hour before or 4 hours after colesevelam
- Oral anticoagulation, both warfarin, and new oral anticoagulation
- Treatment with cyclosporine within two months
- Bowel obstruction (subileus or ileus)
- Biliary obstruction
- Short bowel syndrome
- Bowel ostomy
- Allergy to colesevelam or its constituents
- Allergy to placebo constituents (excluding lactose)
- Investigator-assessed high risk of non-compliance
- If on statin/fibrate medication, unwilling to pause medication between study visits 1 and 2

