## Power calculation

Based on the primary endpoint we assume

- a remission rate of 67% for colesevelam and 27% for placebo (36, 38).
- two-sided  $\alpha = 0.05$ , and  $\beta = 0.20$  (ie. 80% power); and 1:1 allocation.

Thus, we need 23 subjects with BAD in each arm (G.Power 3.1: z-test of two independent proportions).

As we include all patients with diarrhoea regardless of aetiology, the fraction or prevalence of BAD amongst these eligible patients is crucial. Of 71 subjects in our VABAD study, 59 patients had diarrhoea by Hjortswang criteria and deemed by  $C4 \geq 46$  ng/mL, 16 of the 59 had BAD (27%). In comparison with SeHCAT, Borghede et al. found that 41% of patients referred for SeHCAT had primary BAD defined with SeHCAT (44).

Thus to include 2 x 23 patients with BAD defined with  $C4 > 46$  ng/mL, we need

$$\frac{2 \times 23 \text{ BAD subjects}}{27\% \text{ BAD subjects among patients with diarrhoea}} = 170 \text{ patients with diarrhoea.}$$

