**Start of intervention and possibility for delay of intervention**

If the time/hour of the day for visit 2 enables the subject to take two doses of the medication this day, the intervention may start on visit 2, which subtracts one day from the time schedule below.

For logistic reasons in the collaboration between the Department of Nuclear Medicine and the Department of Gastroenterology at the local study centre, the treatment start may be delayed for a maximum of seven days. In case the start is postponed, the postponed days are not counted as study days.

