**Study Diary 2 – treatment period**

This diary registers the number of daily stools and consistency according to the Bristol stool form. The participants also note any AEs. The Study Diary 2 is commenced at Study Visit 2 and entails three periods

1. Study Visit 2 (Study day 8)
2. Run in period of five days (Study day 9 – 13)
3. Registration of Primary endpoint (Study day 14 – 20)

These periods are not separated in the diary. The diary also forms the subject's study participation card, with contact information to the relevant investigator or study nurse.

On study day 9, subjects set an "X" in the diary according to what treatment they think they are receiving: a) Colesevelam, b) Don't know, c) Placebo. This is used to assess initial blinding.

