## Adverse events

All adverse events (AEs) and adverse reactions (ARs) are registered by an AE/AR table in the study Case Record Form and documented at study visits as specified above.

Serious AEs (SAE) and serious ARs (SAR) are defined as an AE or AR that is life-threatening or leading to death, that leads to hospitalization or prolonging of hospitalization, that causes seriously or sustained disability or incapacity to work, or causes a congenital anomaly.

All SAEs and SARs will be reported to sponsor as soon as possible and within 24 hours. A SAR that is not expected is deemed Suspected Unexpected SAR (SUSAR). If the event is life-threatening or deadly sponsor reports to the DMA and to the Ethical Committee immediately and within 7 days with follow up within further 8 days.

All other SUSARs are reported to DMA within 15 days of sponsors knowing.

A SAR is deemed SUSAR if not listed in the AE table for colesevelam.

All SAR's are reported to the DMA and the Ethical Committee in yearly reports and after study completion (sooner than 3 months from the last visit, last patient).

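### Statin and fibrate users must pause their drug from visit 1 to visit 2, but adverse event registration starts only at visit 2 and only for subjects with diarrhoea

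*Combined protocol and SAP*

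**What the plan says.** **The pause.** Exclusion criteria rules out a patient: "If on statin/fibrate medication, unwilling to pause medication between study visits 1 and 2". The section on study visit 2 enforces this: "Any violation of alcohol abstinence the day before study visit 2 and of pausing statin/fibrate use leads to exclusion as a protocol violation". Visit 1 is study day 1 and visit 2 is study day 8.

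**Adverse event registration.** It begins at visit 2. For subjects whose baseline diary shows diarrhoea: "Adverse Event registration starts now (study day 8) and includes all subjects with diarrhoea". For the others: "These subjects do not proceed to the intervention, thus, we do not register adverse events for these subjects".

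**General rule.** The Adverse events section says that events are "registered by an AE/AR table in the study Case Record Form and documented at study visits as specified above". A separate sentence there sends all serious adverse events and reactions to the sponsor within 24 hours. It names no start day and does not limit the rule to subjects with diarrhoea.

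**Diary.** Adverse event entries are described only for the second diary: "The participants also note any AEs. The Study Diary 2 is commenced at Study Visit 2".

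**Dosing start.** The first capsule is normally taken on day 9. It may be taken at visit 2 if two doses fit into that day, or, for logistic reasons, "the treatment start may be delayed for a maximum of seven days".

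**The concern.** The trial changes the medication of statin and fibrate users for a week, as a condition of taking part, and the period in which it looks for harm opens when that week closes.

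The reason given for not registering events in subjects without diarrhoea is that they never receive the intervention. That holds for the capsules but not for the pause. Diarrhoea status is settled from the baseline diary at visit 2, and by then these subjects have paused like everyone else.

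Two things are at stake. One is a record of any harm from a procedure that the trial itself requires. The other is a single clear rule for sites. A site that learns at visit 2 of a hospital admission on day 4 finds one section telling it to report every serious event and another telling it that registration had not begun.

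**Working it through.** **Step 1: set the two windows side by side.**

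| | Start | End | Who |
|---|---|---|---|
| Statin/fibrate pause | Visit 1, day 1 | Visit 2, day 8 | All included users |
| Adverse event registration | Visit 2, day 8 | At least 72 hours after treatment ends | Subjects with diarrhoea only |

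The pause lasts 8 − 1 = 7 days, and registration covers 0 of the 7.

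**Step 2: look for text that closes the gap.**

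- The blood sampling and diary check described for visit 2 include no adverse event history for days 1 to 8.
- The baseline diary has no described adverse event entry.
- The general rule in Adverse events refers back to the visits already specified, so it adds no earlier start.
- Risks and nuisances does not mention the pause.
- The six-month follow-up covers the diagnostic work-up, medication against diarrhoea and questionnaires. It could bring an event to light, but it is not adverse event registration.
- An event that lasts beyond day 8 in a subject with diarrhoea could still be noted. One that resolves within the week, or occurs in a subject without diarrhoea, has no described entry.

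**Step 3: scale.** The plan gives no figure for this point, so there is none to reproduce. The one planning figure used is the 170 patients with diarrhoea in Power calculation (46 / 0.27 = 170.4), where the plan states: "As we include all patients with diarrhoea regardless of aetiology, the fraction or prevalence of BAD amongst these eligible patients is crucial". In the earlier VABAD study, 59 of 71 patients (83%) had diarrhoea by the same criteria.

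- Included subjects: 170 / (59/71) = 204.6, about 205.
- Without diarrhoea: 204.6 − 170 = 34.6, about 35.

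The share on a statin or fibrate is not in the documents. I assume 5% to 30%, equal in those with and without diarrhoea.

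| Assumed share | Pausing (204.6 × share) | Person-days (× 7) | Of these, without diarrhoea (34.6 × share) |
|---|---|---|---|
| 5% | 10 | 72 | 2 |
| 10% | 20 | 143 | 3 |
| 20% | 41 | 286 | 7 |
| 30% | 61 | 430 | 10 |

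**Step 4: time between visit 2 and the first capsule.** It is 0 days with a start at visit 2, 1 day on the standard schedule, and 1 + 7 = 8 days with the longest delay. Registration runs throughout, so for most subjects some recorded time comes before any capsule.

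**The case against.** The best defence is that registration is tied to the investigational product. The uncovered time is one week before any study drug, in people who agreed to pause, and the number of events to be expected is small. That limits the weight of the point. It does not answer it, because the pause is also a trial procedure and applies equally to subjects who never reach the capsules.

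Four stronger readings are tempting, and the documents do not support them.

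- **A serious event in the baseline week cannot reach the sponsor.** The serious-event sentence has no start day and could be read as requiring the report. The fault is contradictory instructions, not the absence of a route.
- **The gap is 205 × 7 = 1,435 person-days, with 35 subjects never covered.** Those totals count everyone included. For a non-user, the week consists of sampling, questionnaires, a diary and a day without alcohol, around a SeHCAT test already ordered. The concern applies to those who pause.
- **Events before the first capsule distort the safety comparison.** They fall on both randomised arms alike, a doctor judges relatedness at visit 3, and the plan specifies no pooled table of events by arm. Taking 12 treatment days and 3 days of follow-up, the share of recorded time before dosing is 8/(8 + 12 + 3) = 35% only at the longest delay. It is 1/(1 + 12 + 3) = 6% on the standard schedule and 0% with a start at visit 2.
- **Laxatives and anti-diarrhoeal drugs are stopped at visit 1 in the same way.** Their use is an exclusion criterion, with exceptions for stable psyllium husk and for opioids for pain. No instruction to stop them at visit 1 is written.

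Consent pages are not in the text reviewed, so nothing is inferred about what participants were told.

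**Conclusion.** The concern holds for subjects who pause a statin or fibrate. Events during a medication change that the trial imposes are not systematically recorded, and users without diarrhoea are never covered. The rule that all serious events go to the sponsor conflicts with the two visit 2 subsections and must be reconciled with them.

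The size is uncertain because it rests on three assumptions: a 5% to 30% share of users, the VABAD proportion with diarrhoea, and the planned 170. The facts about the two windows need none of these.

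The gap comes before dispensing. It biases neither the primary endpoint nor the colesevelam–placebo comparison. This is a cheap improvement in safety capture, of minor to moderate weight.

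**What to change.** Align the wording in Subjects without diarrhoea, Subjects with diarrhoea and Adverse events:

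1. Register serious adverse events from visit 1 for all included subjects, so that the 24-hour rule has one stated start.
2. At visit 2, ask once about adverse events linked to the protocol-required pause, and do so before subjects without diarrhoea leave the intervention track.
3. Record the date of each event and of the first capsule, and list events before the first capsule separately from on-treatment events.

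The cost is one question and one form line at an existing visit, a date filter in the safety listing, and a few more events to report. No change to the pause itself is proposed.
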